**Impact of parasitic infections on intestinal epithelial barrier and
immune activation among persons living with HIV in Lilongwe, Malawi**

NCT number NCT05323396
Document Date 02/15/2022

Title: Impact of parasitic infections on intestinal epithelial barrier and immune activation among persons living with HIV in Lilongwe, Malawi

Abbreviated study name: HAPI (HIV And Parasitic Infection) study

Background:

In sub-Saharan Africa (SSA), more than 22 million people are estimated to be co-infected with HIV and helminths¹ and studies within SSA have reported 14-25% of persons living with HIV (PLWH) coinfecting with pathogenic intestinal protozoa^{2,3}. A prior study from Lilongwe, Malawi published in 2007 reported a prevalence of 30% of PLWH coinfecting with intestinal parasitic infection when including both helminths and pathogenic intestinal protozoa⁴. Although treatable, intestinal parasitic infections are underdiagnosed due to lack of testing and inadequate sensitivity of currently used techniques such as light microscopy. Furthermore, reinfection in endemic regions is common. Consequently, co-infection remains highly prevalent.

CD4⁺ T cell recovery has been shown to be lower in patients from sub-Saharan Africa compared to Europeans early after starting cART after adjusting for age, sex, initial regimen, pre-ART CD4⁺ T-cell count, and HIV RNA⁵⁻⁷. This is an indication that factors other than initial HIV disease state contribute to HIV disease progression in these resource-limited, parasitic-endemic settings. A study in Uganda- using the same stool PCR test that we will use in our proposed study- demonstrated significantly lower levels of CD4 cells in patients co-infected with hookworm, suggesting that intestinal parasitic infection could be contributing to the low CD4 count and delayed recovery in resource-limited settings⁸.

Soluble CD14 is a marker of microbial translocation, released upon LPS stimulation⁹. Both sCD14 and soluble CD163 (sCD163) are markers of macrophage and monocyte activation⁹⁻¹¹. Intestinal fatty acid binding protein (I-FABP) is a marker of intestinal permeability and enterocyte turnover¹⁰. Increased levels of each of these- soluble CD14 (sCD14), soluble CD163 (sCD163), and (I-FABP)- have been shown to predict morbidity and mortality in treated HIV infection, including cardiac disease and neurocognitive decline⁹⁻¹⁴. Preliminary data from a study in Houston, Texas, showed increased levels of sCD14 in PLWH co-infected with *Strongyloides stercoralis* when compared to *Strongyloides* negative PLWH, and a correlation of *Strongyloides* IgG levels with sCD14 and sCD163 levels¹⁵.

Characterizing the effects of intestinal parasitic infections on HIV disease will provide clarification as to whether periodic deworming would improve CD4+ T cell recovery and decrease inflammation in PLWH, and will highlight key pathways to explore for optimizing the health of PLWH worldwide. The impact on systemic inflammation and intestinal damage may have consequences for the long-term risk of serious non-AIDS events.

Objectives:

The **overall goal** of our research program is to determine if periodic deworming of persons living with HIV in intestinal parasite-endemic regions will lead to decreased morbidity and mortality associated with HIV by reducing immune activation and intestinal damage associated with these diseases. Our hypothesis for this project is that intestinal parasitic infections contribute to a modifiable pro-inflammatory state in PLWH.

Aim 1: Determine the prevalence of intestinal parasitic infections in PLWH receiving care at an HIV-treatment center in Lilongwe, Malawi using a highly sensitive multi-parallel stool PCR test. Hypothesis: highly sensitive stool PCR testing will demonstrate that disease burden of parasitic infection in PLWH in Malawi is higher than historically reported based on light microscopy.

Aim 2: Determine the impact of parasitic infection and eradication on intestinal damage and immune activation by measuring sCD14, sCD163, and intestinal fatty acid binding protein (I-FABP) in PLWH before and after treatment of parasitic co-infection. Hypothesis: plasma biomarkers reflecting intestinal damage and immune activation are elevated in those with HIV and parasitic co-infection compared with parasite negative participants with HIV, and these biomarkers decrease with anti-parasitic treatment.

Few studies have evaluated the effect of eradication of intestinal parasitic infection on PLWH on suppressive ART¹⁵⁻¹⁶, and fewer have been prospective studies. We will use a modern molecular diagnostic and quantitative technique, the multi-parallel real-time quantitative PCR (qPCR), which detects and quantifies the burden of 9 common GI parasites including helminths and protozoa simultaneously, with more than 10 times higher sensitivity compared to traditional microscopy⁸. This assay has been optimized at the US National Institutes of Health (NIH) and field tested in Ecuador, Colombia, Mozambique, Argentina, and Uganda^{8,17,18}. Our test will be modified to include PCR for *Schistosoma mansoni*, given the high prevalence of intestinal schistosomiasis in Malawi. This improved sensitivity will overcome the deficiencies of microscopy that have plagued previous studies, resulting in under-diagnosis of parasitic infections and contamination of parasite-negative groups with undiagnosed parasite-infected persons. This approach will facilitate learning the prevalence of parasitic infections, maximize our ability to ensure a truly parasite-uninfected control group, and enable us to assess the impact not only of the presence of intestinal parasites but also the impact of intestinal parasite burden on HIV infection. Comparison of sCD14, sCD163, and I-FABP levels in PLWH with and without parasitic infections, and repeated measurements after eradication will provide data on the impact of intestinal parasitic infections on systemic immune activation and intestinal permeability. Outside of preliminary data from our study performed in Houston, Texas¹⁵, these markers of systemic immune activation and intestinal damage have not been explored in PLWH on ART with parasitic coinfection.

In accordance with the SMART objectives, our goals are specific, measurable, achievable, relevant, and time-bound. The laboratory data obtained by qPCR, *Strongyloides stercoralis* IgG, sCD14, sCD163, and I-FABP are specific and easily measured. The estimated patient enrollment is achievable in the outlined period of time based on the number of patients that regularly receive clinical care at the participating clinics. Once the data are obtained, our research question is achievable with the power calculations outlined above. The relevance of our research question is highlighted by the fact that intestinal parasitic infections may be a modifiable pro-inflammatory state in PLWH contributing to increased morbidity and mortality of this vulnerable population.

Literature Review:

I. HIV and intestinal parasitic coinfection

In sub-Saharan Africa, more than 22 million people are estimated to be co-infected with HIV and helminths¹ and regions of SSA have reported 14-25% of PLWH coinfecting with pathogenic intestinal protozoa^{2,3}. One study from Ethiopia reported as many as 59.8% of PLWH coinfecting with intestinal parasitic infections when including both helminths and protozoa¹⁹. A prior study from Lilongwe, Malawi published in 2007 reported a prevalence of 30% of PLWH coinfecting with intestinal parasitic infection⁴.

Although treatable, intestinal parasitic infections are underdiagnosed due to lack of testing and inadequate sensitivity of currently used techniques such as light microscopy. Furthermore, reinfection in endemic regions is common. Consequently, co-infection remains highly prevalent.

II. Delayed CD4+ T cell recovery in PLWH in intestinal parasite-endemic regions

CD4+ T cell recovery has been shown to be lower in patients from sub-Saharan Africa compared to Europeans early after starting cART⁵⁻⁶. CD4+ T-cell counts after 3 years of ART were higher in people from North America (529 cells/mm³) compared to East Africa (437 cells/mm³), West Africa (494 cells/mm³), Southern Africa (515 cells/mm³), and Asia (503 cells/mm³) after adjusting for age, sex, initial regimen, pre-ART CD4+ T-cell count, and HIV RNA²⁰. In a study from East Africa, 63% of adults had CD4+ T-cell counts < 500 cells/mm³ and 40% had CD4+ T-cells < 350 cells/mm³ after 5 years of ART⁵. Similarly, in a Ugandan cohort, 49.1% of adults had CD4+ T-cells ≤ 400 cells/mm³ after 5 years of ART⁶. Five years of ART increased CD4+ T-cell counts from a median of 114 cells/mm³ to 395 cells/mm³ in a consortium of participants from low-income countries in Africa, Latin America, and Asia²¹. This is an indication that factors other than initial HIV disease state contribute to HIV disease progression in (PLWH) in these resource-limited, parasitic-endemic settings.

III. Impact of parasitic infection on the immune system

Parasitic infections induce Th2 immune responses, characterized by high IgE titers and eosinophil recruitment^{22,23}. Consequently, the Th1 response in someone with parasitic infection is often impaired²⁴⁻²⁶. One study showed that mice with chronic infection with the roundworm *Trichinella spiralis* and acute norovirus infection, the frequency and polyfunctionality of norovirus-specific CD4⁺ and CD8⁺ T-cells were decreased and virus burden increased compared to non-*Trichinella* infected mice²⁷. Mice with chronic infection with the hookworm *Heligmosomoides polygyrus bakeri* had impaired antigen-specific and polyfunctional responses to norovirus²⁷. Similar results were observed with influenza virus in *Trichinella spiralis* infection²⁶. These data indicate that parasitic infections impair virus-specific CD4⁺ and CD8⁺ T-cell responses and may facilitate virus replication.

Intestinal parasitic infections induce immune activation as demonstrated by the following studies: *Trichuris* infection upregulates CCR5 expression on CD4⁺ T-cells²⁸, and hookworm, *Trichuris*, and *Ascaris* induce HLA-DR expression on CD4⁺ and CD8⁺ T-cells²⁸⁻³⁰. *Trichuris* and *Ascaris* treatment downregulates CCR5 expression on CD4⁺ T-cells and HLA-DR expression on CD8⁺ T-cells¹⁷. Hookworm also decreases CD3⁺ and CD4⁺ populations likely due to increased T-cell apoptosis and decreased T-cell proliferation²⁹⁻³². Among HIV-uninfected South Africans, the frequency of HLA-DR⁺ CD8⁺ T-cells and expression of CCR5 on CD4⁺ T-cells decreased 3 months after albendazole and praziquantel treatment of hookworm and *Trichuris* infection²⁸. In summary, intestinal parasitic infections seem to increase T-cell activation, increase CCR5 expression, induce T-cell apoptosis, and suppress T-cell proliferation.

IV. Potential impact of parasitic infections on HIV

Recurrent enteric parasitic infections cause impaired gut healing^{29,30} and increased microbial translocation³⁰⁻³², increased activation of macrophages³³, and intestinal fibrosis^{34,35}. Parasitic infections increase CCR5⁺ CD4⁺ T-cell frequency, creating more HIV targets in HIV-infected persons^{16,26}. Parasitic infections also increase CD8⁺ T-cell activation²⁴. Malnutrition, weight loss, chronic diarrhea, and changed immune responses caused by the intestinal parasitic infections may further accelerate HIV/AIDS progression^{1,36-39}. In a reciprocal manner, HIV infection may impair the immune system's ability to defend against parasitic infections^{40,41}.

Some studies have shown that patients living with HIV (PLWH) with parasitic coinfection have weakened CD4 recovery^{8,30,42,43} and/or higher HIV viral loads^{44,45} compared to those without parasitic coinfection, yet the data are inconsistent. HIV-infected persons in Southern Ethiopia not taking ART who were treated for *Ascaris lumbricoides* had a significant increase in CD4⁺ T-cells from 469 to 551 cells/mm³ at 6 months, compared to a non-significant decrease in helminth-uninfected participants⁴⁶. Similar results were observed in a randomized, double-blind, placebo-controlled trial in ART-naïve Kenyans treated for *Ascaris lumbricoides*⁴⁷. A study in Uganda- using the same stool PCR test that we will use in our proposed study- demonstrated significantly lower levels of CD4 cells in patients co-infected with hookworm, suggesting that intestinal parasitic infections could be contributing to the low CD4 count and delayed recovery in resource-limited settings⁸. Higher HIV viral loads were observed in pregnant women with hookworm or *Trichuris* infections⁴⁴. Deworming of *T. trichiura* or hookworm in an observational study increased CD4⁺ T-cell counts and decreased the percentage of pregnant women on ART with detectable HIV viral load⁴⁵.

In contrast to the studies above, meta-analysis of randomized controlled trials of antiparasitic medications or placebo in HIV-infected people with unknown parasitic infection status showed no significant effect of one-time or repeated deworming on viral load or CD4⁺ T-cell count in people not taking suppressive ART⁴⁸. A retrospective, observational study, empiric deworming did not increase CD4⁺ T-cell counts among Ugandans on ART except when restricted to women in the first year of ART⁴⁹. A study published in 2007 conducted in outpatient clinics in the same setting as our study- Lilongwe, Malawi- found no improvement of HIV viral load after treatment of parasitic infection in PLWH⁴.

Even with the studies above, there are gaps that remain in the question of the impact of intestinal parasitic infection on HIV. Few of the studies are prospective, controlled trials involving treatment of intestinal parasitic infection. Additionally, most of the studies above used low-sensitivity light microscopy to identify those with parasitic infection. Given the low sensitivity of light microscopy, the cohort of patients identified as parasite-

negative likely included a notable number of patients with unidentified parasitic infections. Third, studies of parasitic infections in PLWH on suppressive ART are limited. Our proposed study will help to address the gaps identified in this topic of PLWH and parasitic coinfection.

V. Impact of chronic immune activation and intestinal damage on morbidity of PLWH

In HIV infection, enterocyte loss, tight junction destruction, CD4⁺ T-cell depletion, decreased intestinal mucosal IgA, bacterial overgrowth, and dysbiosis result in increased translocation of pro-inflammatory bacterial products such as LPS^{9,50}. Non-human primate models have illustrated that this gut destruction and microbial translocation begins in the first week of infection^{51,52}. Increased microbial translocation results in increased T-cell and monocyte activation, increased production and recruitment of HIV target CD4⁺ T-cells, and increased lymphatic tissue fibrosis^{50,52,53}. Early suppression of microbial translocation and inflammation in SIV infection reduces immune activation, decreases SIV replication, and preserves intestinal CD4⁺ T cells⁵⁴. In sum, increased microbial translocation is a key driver of immune activation and inflammation in HIV infection.

Soluble CD14 (sCD14) is a marker of microbial translocation, released upon LPS stimulation⁹. Both sCD14 and soluble CD163 (sCD163) are markers of macrophage and monocyte activation⁹⁻¹¹. Intestinal fatty acid binding protein (I-FABP) is a marker of intestinal permeability and enterocyte turnover¹⁰. Increased levels of each of these- soluble CD14 (sCD14), soluble CD163 (sCD163), and (I-FABP)- have been shown to predict morbidity and mortality in treated HIV infection, including cardiac disease and neurocognitive decline⁹⁻¹⁴. One study analyzing 74 participants from the Strategies for Management of Antiretroviral Treatment (SMART) trial who died and 148 matched controls found that participants with the highest quartile of soluble CD14 (sCD14) levels had a 6-fold increased risk of death compared to participants with the lowest quartile, even after adjusting for CD4⁺ T-cell count and other inflammatory markers⁹.

HIV-uninfected South Indians with hookworm have higher LPS, sCD14, endotoxin core IgG, and I-FABP levels compared to hookworm-negative persons from the same village, and LPS and sCD14 levels decreased after documented parasite clearance with treatment⁵⁵. Preliminary data from our pilot study in Houston, Texas, showed increased levels of sCD14 in PLWH co-infected with *Strongyloides stercoralis* when compared to *Strongyloides* negative PLWH, and a correlation of *Strongyloides* IgG levels with sCD14 and sCD163 levels¹⁵.

As demonstrated in the literature referenced above, HIV infection and recurrent enteric parasitic infections have each been shown to be independent causes of intestinal damage, increased microbial translocation from the gut, and immune activation; all of which contribute to a pro-inflammatory state that may drive chronic diseases more prevalent in the HIV-positive population. Characterizing the effects of intestinal parasitic infections on HIV disease will provide clarification as to whether periodic deworming would improve CD4⁺ T cell recovery and decrease inflammation in PLWH, and will highlight key pathways to explore in order to optimize the health of PLWH worldwide. The impact of parasitic infection on systemic inflammation and intestinal damage may have consequences for the long-term risk of serious non-AIDS events.

Methodology

Research Design

This is a prospective study in which participants will be enrolled in outpatient HIV clinics associated with Kamuzu Central Hospital in Lilongwe, Malawi, where there are over 25,000 patients in care with over 90% virally suppressed on ART.

Subjects and Methods

Inclusion criteria include the following: Age ≥ 18 years; HIV-1 infection; currently living in Malawi; on ART ≥ 1 year with undetectable HIV RNA level at the last evaluation, and willingness to be treated with anti-parasitic therapy if infection with intestinal parasite is identified. Exclusion criteria include the following: Inflammatory bowel disease; gastrointestinal tract malignancy; major intestinal surgery during prior 2 years; use of antibiotics other than prophylaxis with trimethoprim-sulfamethoxazole within 60 days of screening; use of antiparasitic medication (ex- albendazole, praziquantel) in the last year; coinfection with

Mycobacterium tuberculosis; pregnancy, breastfeeding mother, or planning pregnancy. The last two are included in exclusion criteria because of the potential risk of teratogenicity with the antiparasitic medications used for treatment and because these can affect the markers of immune activation that we are measuring as a part of the study.

Any subject meeting inclusion criteria and lacking exclusion criteria who is currently receiving care at the clinics affiliated with Kamuzu Central Hospital or Bwaila Hospital will be eligible to participate in this study. Subjects will be given time to ask questions, and if agreeable they will sign consent and then study procedures will be initiated. The investigator will keep the original consent form as part of the study records, and a copy will be provided to the subjects. A pregnancy test will be performed on all women of childbearing years.

After informed consent is signed, a total of 10ml of blood, 20g stool sample, and 20mL urine sample will be collected. Subjects will be given an explanation about hygienic collection of stool samples. They will be given a clean, plastic, wide-mouthed, leak-proof container (of about 125 mL) with a snap-on lid. In addition, each subject will receive a pair of gloves and a small biohazard plastic bag. All subjects will be asked to put 5-25 g of stool in the container (which is approximately 1/5 of the volume content), close the lid and return the container to investigators in the biohazard bag. Each participant will be asked a series of questions (Participant information sheet attached).

Clinical variables including age, sex, CD4+ T-cell count, and CD4% will be collected from the participant's medical chart.

Blood samples will be collected in EDTA-blood collection tubes and centrifuged, then serum will be frozen at -80 degrees at UNC Project Malawi until transport to Houston, Texas. Stool samples will be frozen at -80 degrees until transport to Houston, Texas. Coded serum samples- without personal identifiers- will be sent to the laboratory of [name] at the National School of Tropical Medicine Baylor College of Medicine for determination of levels of immune activation and gut mucosal impairment (sCD14, sCD163, and I-FABP) and *Strongyloides stercoralis* IgG. Stool samples will be processed by stool microscopy in the local UNC Project Malawi laboratory, then the remaining sample will be transported to Houston, Texas to be processed by qPCR for detection of 10 different parasites and quantification of parasite burden at the Laboratory of Parasitology National School of Tropical Medicine Baylor College of Medicine. Urine samples will be brought to UNC Project Malawi for processing and evaluation by microscopy to look for *Schistosoma haematobium*.

The COVID-19 precautions followed by the study team are as follows: all subjects will complete a clinical questionnaire before entry into the clinic. Only those with low risk for current infection with SARS-CoV-2 will be approached for the study. All clinical team members will be wearing gloves and a surgical mask at the time of participant enrollment. All patients are required to wear a mask in the clinic and will be given gloves when they are given the stool sample collection kit.

After enrollment is completed, the serum and stool samples will be shipped to Houston, Texas. Stool samples will be processed by multi-parallel real-time quantitative PCR (qPCR) for detection of 9 different parasites and quantification of parasite burden. Parasites to be evaluated include *Ascaris lumbricoides*, *Ancylostoma duodenale*, *Necator americanus*, *Schistosoma mansoni*, *Strongyloides stercoralis*, *Taenia solium*, *Trichuris trichiura*, *Entamoeba histolytica*, and *Giardia lamblia*. Serum will be processed for *Strongyloides stercoralis* IgG, sCD14, sCD163, and I-FABP.

Participants that test positive for parasitic infection will be contacted and appropriate treatment administered according to the local standard of care. Albendazole single 400mg dose will be given for infection with *Ascaris lumbricoides*, *Ancylostoma duodenale*, *Necator americanus*, *Trichuris trichiura*. Albendazole 400mg daily for 5 days will be given for *Strongyloides stercoralis*. Praziquantel single dose 40mg/kg will be given for infection with *Schistosoma mansoni* and *Schistosoma haematobium*. Praziquantel single dose 10mg/kg will be given to treat intestinal infection with *Taenia solium*.

Metronidazole 500mg two times a day x5 days for *Giardia lamblia* and 500mg three times a day x7 days for *Entamoeba histolytica*.

Female participants that test positive for parasitic infection will have a repeat pregnancy test before administration of antiparasitic medication. If newly pregnant on repeat testing, the study team will be referred to her regular medical provider for evaluation, review of diagnostic tests performed by the study, and for potential treatment with antiparasitic medication. Any participant found to be pregnant at this stage will not be included in the comparison of markers of immune activation or the follow up visit since pregnancy can affect these markers of chronic immune activation. Follow up appointments for all non-pregnant participants will be performed 8-12 weeks after treatment and will include repeated blood and stool sample collection. Pregnancy test will be repeated at the follow-up visit. Any participant found to be pregnant at this stage will not be included in the comparison of markers of immune activation since pregnancy can affect these markers of chronic immune activation. The decision for post-treatment period of 8-12 weeks was made based on prior studies of sCD14⁵⁶ and other inflammatory markers⁵⁷ that used a time frame of 12 weeks between intervention and repeat measurement. A third study showed a decrease in sCD163 in the first eight weeks of treatment for HCV, but no change in either sCD14 or sCD163 from week 8 to week 24 following treatment for HCV⁵⁸.

We anticipate enrollment of 100 patients receiving care at the participating clinics during the recruitment period. With an estimated intestinal parasite prevalence of 30%, we predict 30 cases and 70 controls will be enrolled. This estimate is based on a study with similar patient population in the same region in 2007 which reported 17.3% of participants infected with helminth infections and 12.8% with pathogenic protozoal infections⁴. Our prevalence may be higher than this prior study given the increased sensitivity of our stool PCR test. Participants found to be positive at both the initial and follow up visit will be considered reinfected rather than treatment failure. These will be included in the analysis of prevalence, but the change in markers of immune activation will not be measured in this group since parasite clearance not established. Using Student's unpaired t-test to compare mean values of biomarkers between study groups, we will have 80% power to detect a difference of 0.434 x10⁶ pg/ml, 0.56 mg/l, and 598 pg/ml between groups for biomarkers sCD14, sCD163, and I-FABP, respectively with effect sizes within the range of prior studies^{9,14,59}. Using paired t-tests to compare pre- and post-treatment biomarker levels, we will have 80% power to detect post-treatment changes of 0.317 x10⁶/ml, 0.41 mg/l, and 435 pg/ml in sCD14, CD163, and I-FABP respectively⁶⁰. A sample size less than 100 increases the chance of a type II error where a true difference in markers of chronic inflammation does not reach clinical significance. A sample size of greater than 100 should not be necessary given the estimated findings in our patient population and the data presented by the studies cited above. A sample size of 100 should be easily attainable in a reasonable amount of time (4-8 weeks) without the unnecessary use of additional resources.

Clinical variables including age, sex, and most recent CD4 count will be recorded. Clinical predictors of parasitic infection (eg CD4%) will be determined using multivariable logistical regression. Univariable linear regression will be used to determine associations between markers of immune activation (continuous outcome variable) and predictors including the clinical variables above as well as presence of multiple parasitic infections.

Study visits:

- v0= Screening visit: includes explanation of study, inclusion/exclusion criteria, sign ICF
- v1= Baseline visit: complete CRF; collection of blood, stool, and urine samples
- v2= Treatment visit: only for those participants positive for parasitic infection
- v3= Post-treatment/follow-up visit performed 8-12 weeks after administration of antiparasitic therapy to those participants found to be parasite-positive. Sample collection from controls (parasite-negative participants) will be done in a similar time window.

*screening and baseline visits can be done the same day

**Participants positive for parasitic infection will complete v0, v1, v2, v3. Participants negative for

parasitic infection will not have v2. Full participation in the study for a parasite negative participant includes completion of v0, v1, v3.

***Participants will be reimbursed for v1, v2, v3.

Ethical Considerations

In addition to the Malawi National Health Sciences Research Committee, we will submit for IRB approval from University of North Carolina School of Medicine, and the National School of Tropical Medicine at Baylor College of Medicine. Participation in the study will be voluntary. All study participants will be explained the study design and all questions answered before the participant provides written, informed consent.

Neither the investigator, nor any research team member will coerce or unduly influence nor specifically target vulnerable subjects to participate in the study. Research subjects will be informed that participation is voluntary and that they are free to withdraw from the study for any reason at any time. Subjects will be given time to ask questions, and if agreeable they will sign consent and then study procedures will be initiated. The investigator will keep the original consent form as part of the study records, and a copy will be provided to the subjects. A Chichewa translator will be present for the entirety of each interaction with each participant.

The possibility of a breach in confidentiality will be minimized by limiting the number of people that will have access to the information, the use of coded data, and the stringent security measures that will be utilized. Only [name] and members of the research team will have access to the patient clinical data. The Participant Information Sheet with clinical information will only have the participant codes and deidentified clinical information. The informed consent forms and the "link-log form" with patient names and patient codes will be kept in a locked cabinet at UNC Project Malawi. Information entered into the electronic database will only include the participant identification number. The patient names will not be included in the electronic database. The database will not be saved on personal computers, rather will only be saved to a secure UNC server and will be password protected.

Work Plan

We plan to begin enrollment of participants starting January 2022. We estimate that 2-3 months will be sufficient to recruit 100 participants. After 100 participants are enrolled and samples collected, we will send samples to Houston, Texas. We expect it will take 1-2 months to process all of the samples in the laboratory of [name]. Follow up visits will take place 2-3 months after participants with parasitic infections were treated. Once follow up visits completed and samples obtained, the second shipment of samples will be sent to Houston, Texas. We expect another 1-2 months for the processing of samples in the laboratory of [name]. Once all samples are processed, laboratory analysis can be performed. A manuscript will be prepared and submitted for publication. An infectious diseases journal will be the target for publication of the manuscript. The NHSRC will be provided a copy of the manuscript. Additionally, we plan to present our findings at both a local and an international academic conference.

VI. References

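### The baseline marker comparison between infected and parasite-negative participants is an unadjusted t-test, although infection is observed rather than randomised and age and sex are recorded

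*Combined protocol and SAP*

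**What the plan says.** Aim 2 (Objectives) sets out to "Determine the impact of parasitic infection and eradication on intestinal damage and immune activation". Its between-group hypothesis is that the markers "are elevated in those with HIV and parasitic co-infection compared with parasite negative participants with HIV".

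The analysis is described at the end of Methodology, Subjects and Methods:

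- **Between-group contrast.** The plan names Student's "unpaired t-test to compare mean values of biomarkers between study groups". The words stand in the power statement, but no other analysis of this contrast is given anywhere.
- **Group sizes.** "we predict 30 cases and 70 controls will be enrolled", on an expected prevalence of 30%.
- **Regressions with a marker as outcome.** These are specified as univariable, with "predictors including the clinical variables above as well as presence of multiple parasitic infections".
- **The only multivariable model.** "Clinical predictors of parasitic infection (eg CD4%) will be determined using multivariable logistical regression". Here infection is the outcome, not a marker.
- **Covariates available.** "Clinical variables including age, sex, CD4+ T-cell count, and CD4% will be collected" from the medical chart.

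**The concern.** The groups are defined by a test result. They are not randomised, matched or stratified. A difference in mean marker level may therefore partly reflect who becomes infected, and confounding of this kind can create a difference or hide one.

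Eligibility removes some of the risk: at least a year on ART with undetectable HIV RNA, no recent antibiotics or antiparasitics, no tuberculosis, no pregnancy. It does nothing about sex, and limits age only to 18 or over.

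Age, sex and CD4 each enter a model with infection or with a marker, but no model contains a covariate, infection and a marker together. Adding infection status to the univariable set would not help, because a linear regression on one binary predictor is the same test as the unpaired t-test.

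At stake is whether Aim 2's first hypothesis can be read as saying anything about infection. The Literature Review itself, in the section on delayed CD4 recovery, cites a regional comparison made "after adjusting for age, sex, initial regimen" and other factors. That comparison concerns CD4 rather than these markers, so it illustrates the principle and no more.

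**Working it through.** **Inputs.** From the plan: 30 infected, 70 parasite-negative, 80% power, detectable differences of 0.434 ×10⁶ pg/ml (sCD14), 0.56 mg/l (sCD163) and 598 pg/ml (I-FABP). Not in the plan: alpha, marker SDs, covariate imbalances and covariate–marker correlations. A two-sided 5% test is assumed.

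**Step 1: the plan's own figures.** The standard error of the difference, in SD units, is √(1/30 + 1/70) = 0.218, with 98 degrees of freedom. From the noncentral t distribution, 80% power requires a standardised difference of d = 0.617. The implied SDs are:

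- sCD14: 0.434 / 0.617 = 0.703 ×10⁶ pg/ml
- sCD163: 0.56 / 0.617 = 0.907 mg/l
- I-FABP: 598 / 0.617 = 969 pg/ml

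Without a stated SD or alpha, the plan's figures can be back-solved in this way but not independently confirmed.

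**Step 2: effect of an assumed confounding bias b (in SD) on the unadjusted test.** With no true effect, the rejection rate comes from a noncentral t with noncentrality b / 0.218. With a true difference of 0.617 and bias in the opposite direction, the noncentrality is (0.617 − b) / 0.218.

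| b (SD) | b / 0.617 | False positives | Power, opposite bias |
|---|---|---|---|
| 0.02 | 3% | 5.1% | 77% |
| 0.06 | 10% | 5.9% | 72% |
| 0.1 | 16% | 7.4% | 65% |
| 0.2 | 32% | 15% | 47% |
| 0.3 | 49% | 28% | 30% |

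In the plan's units, 0.02 to 0.3 SD is 0.014 to 0.21 ×10⁶ pg/ml sCD14, 0.018 to 0.27 mg/l sCD163 and 19 to 291 pg/ml I-FABP. If 20 of 100 are infected, false positives run from 5.1% to 22% over the same biases; if 50 of 100 are infected, from 5.1% to 32%.

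**Step 3: what such a bias requires.** For a binary factor such as sex, b = imbalance × effect. A 10-point imbalance with a 0.3 SD effect gives 0.03 SD and 5.2% false positives. Twenty points with 0.5 SD gives 0.10 SD and 7.4%. Thirty points with 0.8 SD gives 0.24 SD and 19%.

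**Step 4: what adjustment recovers.** Ordinary least squares was simulated (40,000 runs) with one continuous covariate plus sex in the model. The bias is the covariate's group difference times its slope on the marker.

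| Difference × slope | False positives, unadjusted → adjusted | Power with opposite bias, unadjusted → adjusted |
|---|---|---|
| 0.2 × 0.1 = 0.02 | 5.1% → 5.0% | 77.2% → 79.2% |
| 0.3 × 0.2 = 0.06 | 5.8% → 5.0% | 71.2% → 79.5% |
| 0.5 × 0.2 = 0.10 | 7.4% → 5.0% | 65.8% → 79.0% |
| 0.5 × 0.4 = 0.20 | 14.7% → 5.1% | 47.6% → 83.7% |
| 0.75 × 0.4 = 0.30 | 27.3% → 4.8% | 30.0% → 81.7% |

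This is the favourable case, with the confounder in the model. If half of a 0.2 SD bias comes from an unmodelled factor, false positives fall only from 15% to 7.4%, and power rises only from 47% to 64%.

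**The case against.** The best reply is that the t-test appears in a sample-size sentence. Sizing a study on a simple test is common and does not rule out an adjusted analysis. That is fair as a description of the sentence, but the plan gives no other method for the contrast, so the sentence is all there is to follow.

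A second reply is that the two sets of regressions would show whether age or sex is related both to infection and to the markers, so confounding need not go unnoticed. This also has some force. It is assessment without adjustment, however, and leaves the choice of any adjusted model until the results have been seen.

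Third, materiality is unproven. The documents give no imbalance and no covariate–marker association, and the large figures need 0.2 to 0.3 SD of bias. Through sex alone, 0.2 SD would take a 20-point imbalance and a 1 SD effect. This stands, and it is why the consequence can only be given as a range.

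Fourth, the participant information sheet mentioned in Subjects and Methods is not in the available text, so other confounders may be collected. That could justify a longer covariate list. It does not remove the case for age and sex.

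**Conclusion.** The concern holds for the baseline, between-group half of Aim 2. As written, the contrast is unadjusted although the exposure is observed and two obvious covariates are already recorded. That much is certain from the text. The consequence is not: depending on the assumed bias it is negligible (about 5% false positives and 77% power at 0.02 SD) or material (28% and 30% at 0.3 SD). These figures assume 30 against 70, a two-sided 5% test and SDs implied by the plan's own detectable differences. The plan should be changed, but nothing in the documents shows that its conclusion would be wrong without the change.

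**What to change.** Make the main baseline comparison, for each marker, a prespecified linear regression on infection status adjusted for age and sex. Report the adjusted mean difference with a 95% confidence interval in the units of the power statement. Put CD4 in a prespecified sensitivity model only: the Background and the section on parasitic infections and HIV both suggest that infection may lower CD4, so it could be a consequence of infection rather than a confounder. Keep the unadjusted comparison as supportive, preferably with Welch's test because the groups are unequal in size. Log transformation and robust standard errors are optional. Describe the result as an association, since unmeasured confounding remains.

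The cost is wording and about 2 of 98 degrees of freedom, with no new data. Against 80% power for the unadjusted test, simulated power of the adjusted model is:

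- about 79% if the covariates are balanced and unrelated to the marker;
- 77% or 74% if a covariate unrelated to the marker differs by 0.5 or 0.75 SD between groups;
- 86% if a balanced covariate correlates 0.4 with the marker.

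A three-covariate model that includes CD4 could fall to 71% if the covariates explain 20% of infection status and none of the marker. Using Welch's test for the supportive comparison costs about 0.4 points of power when the SDs are equal.
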